4. CDR = 0.5
5. WTAR and HVLT scores that screen the participant in (see: *I:\Cores\DMB\[name] STUDIES\PATH-MCI\HVLT and WTAR Scoring*)
6. English speaking.
7. Capacity to consent.

Exclusion Criteria:

1. Age is less than 60 or greater than 85 years old.
2. CDR \neq 0.5
3. MADRS score < 7 or > 30
4. WTAR and HVLT z-score difference > -1.5
5. Change in antidepressant, cholinesterase inhibitors or memantine in the last 12 weeks prior to start of study and/or with medical recommendation to adjust dosage in the next 3 months (during treatment)
6. Current involvement in psychotherapy
7. Deemed to have a significant suicide risk
8. Deemed too unstable medically, psychiatrically or neurologically to safely enroll
9. Lack of English fluency
10. No available study partner
11. Screening incomplete

INTERVENTION

PATH-MCI:

PATH-MCI follows the process model of emotion regulation. According to this model, emotions such as those associated with depression, can be regulated with five broad strategies: situation selection (selecting the situations a person is exposed to), situation modification (changing potentially emotion-eliciting situations), attentional deployment (shifting one's attention within a situation), cognitive change (changing how one thinks about a situation), and response modulation (utilizing direct efforts to alter one's emotional responses). In conjunction with these strategies, PATH-MCI incorporates a simplified problem-solving approach, compensatory strategies, environmental adaptations and significant other involvement to achieve emotion regulation. At the end of treatment, PATH-MCI therapists provide to patients a personalized summary of treatment that highlights the problems that were addressed and the successful techniques that were used to solve them.

Comparison Condition: Supportive Therapy:

ST is a control intervention not aimed to improve emotion regulation. The ST therapist strives to create a positive alliance with the patient by emphasizing non-specific therapeutic interactions and techniques that convey to the patient, interest, concern and understanding. For the purposes of this study, an effort will be made to avoid all emotion regulation techniques that relate to PATH-MCI.

FOLLOW-UP ASSESSMENTS

Follow-up assessments are conducted by the WCM RA at 6, 12, 24, 36 and 52 weeks after the baseline and include measures of mood, cognition and suicidal ideation. Patients will receive \$30 (cash, check or gift card) as compensation for assessment completion at each time point. Study partners will receive \$20 (cash, check or gift card) as compensation for assessment completion at each time point.

PROCEDURES FOR TREATMENT AFTER STUDY COMPLETION

Patients whose follow-up assessments indicate a need for continued mental health services will be provided with mental health referrals.

DATA MANAGEMENT

Data will be collected by the study RA at baseline and at follow-up assessments. The RA also will be responsible for writing and presenting patient summaries to the PI. The social worker will complete updates on the progress of their therapy sessions. [name] manages the PATH-MCI database and weekly reporting.

Research records will be kept confidential to the extent permitted by law. Patients will be assigned ID numbers by the PATH-MCI study team, and all identifying information will be removed from records that are submitted to Weill Cornell Medicine for data analysis. Paper research records will be kept in locked file cabinets. When necessary for purposes of auditing, the Cornell IRB, NIMH, and all Federal oversight agencies will be provided access to these files. Computers will be password-protected, and all staff participating in the study will be trained in protecting human subjects in research. Data will be published in aggregate form without unique identifiers. No analyses will be published in which it is possible to identify individuals based on data.

SUSTAINABILITY

[name] will train two LCSWs in PATH-MCI (or more if needed). Training will consist of a one-day workshop with didactics, role-play and review of previously audiotaped sessions. After the workshop, the therapist will administer 6 PATH-MCI sessions to 2 pilot patients during the first four months. To be certified in PATH-MCI, therapists must achieve a score of greater than or equal to 4 (very good) out of 5 on the PATH-MCI Adherence Scale.

Conducting the Study Remotely

Due to COVID-19, and other circumstances where a patient would not be able to be seen in person, the study may take place remotely. E-consenting can take place via REDCap if the patient has access to Internet. The consenting process would be the same as in-person consent, with a member of the study team speaking with the patient over the phone or videoconference to explain the consent in detail. The consent form may also be mailed to the potential participant with a self-addressed stamped envelope to return to the study team.

Research assessments and both interventions (PATH-MCI and ST-CI) can take place over the phone and/or videoconference. Therapy visits will be conducted in a private room (home or office) and sessions will be recorded only if subjects have consented to that.

Research assessments will also take place in a private room with no one else present; if patients do not have access to video, some assessments may not be able to be completed in full. Please reference most recent Assessment Grid for list of assessments that can be done remotely and via which method (phone and/or video).

If the study is being conducted remotely, the genetics blood draws cannot be done.

PROTOCOL FOR ASSESSING AND DOCUMENTING SUICIDAL IDEATION

Emotion, Cognition, and Psychotherapy Lab

[name]

If suicidal ideation is expressed during the assessment research assistant should:

1. Complete Suicide Risk Assessment (SRA) or
2. Start SRA; finish completing it based on information from clinical evaluation

PASSIVE SUICIDAL IDEATION EXPRESSED TO RESEARCH ASSISTANT

CSSRS=1 (wish to be dead, wish to not wake up) or having thoughts that life is not worth living

Action Step 1: Research Assistant reaches out to clinician.

Action Step 2: Clinician speaks with patient to evaluate them either in person or by phone.

PATIENT ASSESSED AS MILD SUICIDE RISK BY CLINICIAN

Action Step: Clinician emails [name] with a brief summary of the situation.*

Action Step: Review & Finalize SRA

The clinician evaluates the following and the RA or clinician include the appropriate language on page 6 (last page) of the SRA:

"The patient has been evaluated and is not in imminent need of hospitalization at this time. Patient confirmed that if the intensity or frequency of thoughts increased, they would take appropriate action (ie, speak with family, call 911, go to the ER.) SRA completed in collaboration with... and reviewed by"

[name], [name], or Dr.

[name] signs the SRA.

Study therapists should include this in the clinical notes as well.

PATIENT ASSESSED AS INTERMEDIATE OR HIGH RISK BY CLINICIAN

- Action step 1: Clinician informs primary clinician (if they are not the treating clinician)
- Action step 2: Clinician reaches out to [name] to evaluate the patient.*
If [name] isn't available then:
 - Clinician reaches out to attending psychologist/psychiatrist to evaluate whether the patient needs hospitalization, or
 - Clinician takes the patient to evaluation center or calls 911

PATIENT ASSESSED AS MILD OR INTERMEDIATE SUICIDE RISK BY SUPERVISING CLINICIAN

PATIENT ASSESSED AS HIGH SUICIDE RISK BY SUPERVISING CLINICIAN

Action Step: Hospitalization required

In Westchester: The clinician and/or the supervising clinician will call the Evaluation Center [contact]) to inform them that there is a patient in need of immediate evaluation and to provide preliminary demographic and clinical information. The clinician and/or supervising clinician will walk patient to EC. If needed, clinician and/or supervisor will call Security to request an escort ([name]).

In Manhattan: The clinician or supervisor clinician will call 911. Notify the front desk in the building lobby [contact]) so they may facilitate entrance of the police/EMS. All clinical information should be provided to EMS by the clinician and/or supervising clinician.

Action Step: Complete SRA

ACTIVE SUICIDAL IDEATION EXPRESSED TO RESEARCH ASSISTANT
C-SSRS ≥ 2 or reports any kind of suicidal behavior (suicide attempt, self-injurious behaviors, interrupted or aborted attempts, preparatory acts)

Action Step 1: Research Assistant reaches out to clinician.

Action Step 2: Clinician evaluates patient in person.

Action Step 3: Clinician or Research Assistant contact primary clinician (if they aren't the primary clinician) and informs them of the situation.

Action Step 4: Research Assistant or clinician reaches out to [name].* [name] evaluates the patient. If [name] isn't available then:

- Clinician reaches out to attending psychologist/psychiatrist to evaluate the patient; or
- Clinician takes the patient to evaluation center or calls 911

PATIENT ASSESSED AS INTERMEDIATE SUICIDE RISK BY CLINICIAN AND SUPERVISING CLINICIAN

PATIENT ASSESSED AS HIGH SUICIDE RISK BY CLINICIAN AND SUPERVISING CLINICIAN

Action Step: Review and Finalize SRA

The clinician evaluates the following and the RA or clinician include the appropriate language on page 6 (last page) of the SRA:

"The patient has been evaluated and is not in imminent need of hospitalization at this time. Patient confirmed that if the intensity or frequency of thoughts increased, they would take appropriate action (ie, speak with family, call 911, go to the ER.) SRA completed in collaboration with... and reviewed by"

[name], [name], or [name] signs the SRA. Study therapists should include this in the clinical notes as well.

* Therapist should have clear information re. the nature of the SI, any consideration of methods, suicide plan, or intent.

Action Step: Hospitalization required

In Westchester: The clinician and/or the supervising clinician will call the Evaluation Center [contact]) to inform them that there is a patient in need of immediate evaluation and to provide preliminary demographic and clinical information. The clinician and/or supervising clinician will walk patient to EC. If needed, clinician and/or supervisor will call Security to request an escort ([name]).

In Manhattan: The clinician or supervisor clinician will call 911. Notify the front desk in the building lobby [contact]) so they may facilitate entrance of the police/EMS. All clinical information should be provided to EMS by the clinician and/or supervising clinician.

Action Step: Complete SRA

If the participant is a patient of one of NYP psychiatric services (eg OPD, partial hospital, inpatient service), these clinical team must be informed of the patient's SI and/or hospitalization. If patient is receiving treatment at the PHP program, additionally notify [name], [contact], [contact]

[figure not shown]
PROTOCOL FOR ASSESSING AND DOCUMENTING SUICIDAL IDEATION

[figure not shown]
Emotion, Cognition, and Psychotherapy Lab

[name]

If suicidal ideation is expressed during the therapy session, the therapist should:

1. Use the SRA assessment as a guideline to evaluate the patient
2. Start completing SRA during the evaluation or complete the SRA after the evaluation based on clinical notes.

Contact Page:

LCSWs:

[name]: [contact] [name]: [contact]
[name]: [contact] [name]: [contact]

Psychologists:

[name]
[contact]
Office: [contact]

[name] [name]
[contact] [contact]
[contact] [contact]
Office: [contact] Office: [contact]

[name] [name]
[contact] [contact]
Office: [contact] Office: [contact]

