1. Finalize the PATH-MCI Manual and establish feasibility of therapist training. We will train 4 LMSW/LCSWs: 2 will be trained in the PATH-MCI therapy, 2 will be trained in Supportive Psychotherapy. We will determine the success rate of training and number of hours needed to achieve PATH-MCI certification.

MONTHS 4-60

[figure not shown]
2. Assess PATH-MCI's reach, feasibility and acceptability: We will assess across conditions:
 - a. Reach: Number of patients screened, and those who meet inclusion criteria;
 - b. Feasibility: Number of patients who receive PATH-MCI or ST for mental health care and research procedures (timely referrals, assessments);
 - c. Acceptability: Patient's treatment satisfaction at 6, 12, 24, 36 and 52 weeks.

Benchmarks of the study progress: Feasibility: At least 75% of PATH-MCI participants will complete PATH-MCI. Acceptability: We will obtain treatment satisfaction score at the end of PATH-MCI treatment.

3. Preliminary Effectiveness: Over the course of 52 weeks, PATH-MCI patients, compared to patients receiving Supportive Psychotherapy, will have better global cognition and greater (effect size) and clinically significant reductions in disability and depression. Furthermore, better episodic memory and executive function will mediate the effects on cognitive outcomes

OVERVIEW OF DESIGN

Figure 1.

RECRUITMENT PROTOCOL

1. Patients are assessed and recruited from New York City Locations and Westchester.
 - Patients in NYC will be seen at [name].
 - Patients in Westchester will be seen at [name], Institute of Geriatric Psychiatry.
 - Patients at Montefiore will be seen at [name].
 - Note: There is no compensation for transportation expenses for patients. Any special cases must be discussed with [name] and [name].
 - Patients who are not able to meet in person may be assessed by phone or video.
2. Study staff may recruit using flyers, posters and referrals.
 - Flyers
 - NYC
 - Flyers for the study are placed in the waiting room of doctor's offices at [name], as permitted by the doctor's office. RAs must talk to the front desk before leaving flyers. Preferred floors are the 11th and 12th floors.
 - Flyers also can be placed in the elevators of the main hospital building on 72nd Street. Permission for this has been granted.
 - WP
 - Flyers can be placed in the waiting room of the Institute of Geriatric Psychiatry.

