 - Flyers also may be distributed at events, eg. Salute to Seniors, etc.
 - Posters
 - A poster version of the flyer can be placed in the lobby of the [name] office.
 - RAs must communicate at all times with the building manager, [name]: [contact]. Inform her that we will be placing a poster in the lobby. Confirm with her the schedule for this, and that the easel obtained is the correct one to use.
 - Order posters through [name] or [name].
 - Referrals
 - We obtain referrals from different doctors. I.e. [name].
 - Make sure to follow up with the referral sources and to update referral sources about the patients they referred to us (meet criteria, did not meet, did not reach out to us, etc.).
 - We may also obtain referrals from sources, like the 4331 line at the Institute of Geriatric Psychiatry, and outside sources like JASA.

3. Phone screens

- When calling a potential patient, RA makes sure to first explain the study (quick overview) and answer any questions.

- Proceed with the phone screen, if a patient is interested in the study and agrees to the phone screen. Phone screens must be conducted with patients prior to scheduling a screening appointment
- Phone screen form for PATH-MCI study can be found at *I:\Cores\DMB\[name] STUDIES\Phone Screens*
- RAs must conduct phone screens on days and times that therapists and psychologists at the Institute are available. In case of an emergency, ie. a patient endorses suicidal ideation, the RA must communicate this information immediately to the therapists and psychologists present. RA must follow the suicide risk protocol. (See comprehensive SRA protocol at end of this document.)
- If the patient seems eligible from the phone screen (i.e. endorses some depression and low mood and some memory problems), schedule a screening session with the patient.

STUDY PROTOCOL

1. RAs obtain potential patient information from various referral sources.
2. RA contacts a potential patient to complete a phone screen about memory/neurological problems, mood/depressive symptoms, current involvement in treatment, and medical illnesses.
3. If the individual is interested in participating in our study and does not appear to meet exclusion criteria, the RA will invite the individual to come to our offices in White Plains or NYC, or to schedule a video or phone appointment, depending on the circumstances.

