4. Therapists do not need to ask about new health problems. If the patient spontaneously says something in a session, the therapist should try to get as much of the above information as possible and let the RA know, so that the RA can complete this form.

² As of June 2020, the Westchester Division no longer has a clinical laboratory. Only a certified RA may collect samples at the White Plains site.

SUICIDAL IDEATION/ BEHAVIOR PROTOCOL

When a patient reports passive suicidal ideation on the MADRS Suicide Ideation item or the Scale for Suicide Ideation:

1. Complete a Suicide Risk Assessment
2. Reach out to the patient's study therapist. If the therapist is not available, reach out to [name] or another attending psychologist at the Institute.
3. The clinician will speak to the patient and assess the situation.

When a patient reports active suicidal ideation or any kind of suicidal behavior (suicide attempt, self-injurious behaviors, interrupted or aborted attempts, preparatory acts) on the MADRS Suicide Ideation item or the Scale for Suicide Ideation:

1. Complete a Suicide Risk Assessment.
2. Reach out to the patient's study therapist. RA or therapist also needs to reach out to [name] and inform him about the situation and ask him to assess the patient. If [name] is not available, contact another attending psychologist at the Institute ([name] needs to be informed later on about the situation.)
3. Preferably, the assessment by a clinician is done during the same phone call or when the patient is still in the office.

*Please see comprehensive SRA protocol at the end of this document.

RESEARCH ASSESSMENTS

The RA will describe the study, ask potential patients to sign consent, and administer a screening assessment to evaluate eligibility. Once this is confirmed, the RA will administer a baseline assessment. At this assessment, the RA will explain that follow-up assessments will be administered at 6, 12, 24, 36 and 52 weeks after the baseline assessment. The RA also explains that patients will be compensated \$30 for each set of completed assessments. Caregivers will be compensated \$20 for each set of assessments.

Inclusion Criteria:

1. Have a study partner.
2. Be 60-85 years old.
3. No antidepressants or have been on a stable dose of antidepressants for 12 weeks prior to start of study.

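### For active suicidal ideation reported to the research assistant, Action Step 2 allows only in-person evaluation, which conflicts with the protocol's other suicide-risk text and cannot be done during its phone and video contacts

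*Protocol*

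**What the plan says.** The protocol deals with suicidal ideation reported to the RA in two places.

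- **Suicidal Ideation/Behavior Protocol (main text).** For active ideation or suicidal behaviour on the MADRS suicide item or the Scale for Suicide Ideation: "Preferably, the assessment by a clinician is done during the same phone call or when the patient is still in the office". The section then points to the comprehensive procedure at the end of the document.
- **Protocol for Assessing and Documenting Suicidal Ideation (comprehensive procedure).** The active branch, triggered by a C-SSRS of 2 or more or any suicidal behaviour, reads "Action Step 2: Clinician evaluates patient in person". The passive branch, triggered by a C-SSRS of 1 or thoughts that life is not worth living, reads "Action Step 2: Clinician speaks with patient to evaluate them either in person or by phone".

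The protocol also creates contacts in which the patient is off site.

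- **Recruitment Protocol, item 3:** "Phone screens must be conducted with patients prior to scheduling a screening appointment". If ideation is endorsed there, "the RA must communicate this information immediately to the therapists and psychologists present", and the RA is sent to the comprehensive procedure: "RA must follow the suicide risk protocol. (See comprehensive SRA protocol at end of this document".
- **Recruitment Protocol, item 1:** "Patients who are not able to meet in person may be assessed by phone or video". Study Protocol, item 3, likewise lets the screening appointment be by video or phone.
- **Conducting the Study Remotely** permits research assessments and therapy by phone or video. For the detail it says "Please reference most recent Assessment Grid for list of assessments that can be done remotely and via which method (phone and/or video".

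The comprehensive procedure gives hospitalisation instructions by site, in both the passive and the active branch. At Westchester, staff telephone the Evaluation Center, walk the patient there and ask Security for an escort if needed. In Manhattan, staff call 911 and alert the building's front desk.

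**The concern.** The higher-risk branch has the narrower rule. An RA who hears active ideation by phone or video is directed to a procedure whose evaluation step requires the patient and clinician to be in the same place. A later visit would satisfy the words, but only by delaying evaluation of the more urgent group. The main text treats a same-call evaluation as acceptable and indeed preferable, so staff have two instructions that disagree and must choose between them during a crisis.

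The hospitalisation text raises a related problem. A patient who is at home cannot be walked to the Evaluation Center, and the Westchester paragraph offers nothing else.

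What is at stake is participant safety and a procedure that staff can follow as written. The trial's estimates and error rates are not affected.

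**Working it through.** The protocol gives no figure to reproduce, so the check sets the texts side by side.

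**1. Mode of clinician evaluation**

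| Place | Trigger | Mode stated |
|---|---|---|
| Main text, active | MADRS suicide item or Scale for Suicide Ideation: active ideation or behaviour | Same phone call, or while still in the office (a preference) |
| Comprehensive, passive, Step 2 | C-SSRS 1, or life not worth living | In person or phone |
| Comprehensive, active, Step 2 | C-SSRS 2 or more, or any suicidal behaviour | In person only |
| Comprehensive, active, Step 4 | As above | None stated |

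The passive branch names the phone explicitly, so the active Step 2 is hard to read as shorthand that includes it. The instruments in the first and third rows differ, but both rows cover active ideation or suicidal behaviour reported to the RA, with the same examples of behaviour. The instructions conflict wherever those triggers overlap.

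**2. Can Step 2 be done in the contacts the protocol creates?** The phone screen is mandatory, by telephone, and sent to this procedure. Later assessments may be remote, including where the patient cannot be seen in person. The remote-conduct section makes an exception for genetic blood draws but none for suicide-risk evaluation. In-person evaluation is not possible during any such contact.

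**3. How many contacts are exposed?** At least 1 per candidate, the phone screen. At most, for an enrolled patient: 1 phone screen + 1 screening + 1 baseline + 5 follow-ups (weeks 6, 12, 24, 36, 52) = 8. The upper figure assumes that every assessment may be remote; the Assessment Grid that would settle this is not shown. These are contacts, not ideation events.

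**4. Where is a 911 call by staff written?** In the two Manhattan paragraphs, and in two fallback lists for when the named supervising clinician is unavailable (passive branch judged intermediate or high risk; active branch, Step 4): 2 + 2 = 4 places. The Westchester paragraphs have it in 0 of 2. References to 911 in the standard closing statement describe what the patient would do and are not counted. For an off-site Westchester patient judged high risk by an available supervising clinician, no transport route is written.

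**The case against.** The strongest reply is that, read as a whole, the protocol does not leave an off-site patient without a clinician.

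- **Step 4 of the active branch** has the named supervising clinician evaluate the patient, or an attending psychologist or psychiatrist otherwise. It states no mode and is not made conditional on Step 2. This stands. Only one of two evaluation steps is too narrow, and a reader should not infer that the comprehensive procedure rules out every remote evaluation.
- **Phone screens have live cover.** Clinicians must be available and must be told at once. This stands, and makes the phone screen the best-protected of the remote contacts. It does not reword Step 2.
- **The two suicide sections use different instruments.** This stands: they should not be called identical triggers. The overlap is enough for conflicting instructions.
- **Both hospitalisation paragraphs describe on-site logistics**, and the protocol does not say which governs a patient at home. This also stands. It is a reason to add an off-site instruction for both sites, and it narrows the Westchester point to the case where the supervising clinician is available.
- **The text may be a flattened flow chart.** Risk headings stand next to each other and figures are missing nearby. Step 2 itself is intact, but statements about what is absent from the branches are less secure than those about what is present.

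**Conclusion.** The point holds as an inconsistency in a safety procedure that should be fixed. Step 2 of the active branch conflicts with the main text and with the passive branch, and cannot be performed during remote contacts that the protocol permits. The hospitalisation gap is real but narrower: an off-site patient under the Westchester paragraph, with the supervising clinician available.

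A reader might infer that remote patients with active ideation go unevaluated, or that no emergency route exists for them. The documents do not support either: Step 4, the main text and the phone-screen cover all provide clinician evaluation, and 911 is written for Manhattan and as a fallback. Nor should the range of 1 to 8 contacts be read as a measure of harm. The protocol gives neither an ideation rate nor the share of remote contacts, so the number of patients affected is unknown. It may be small, because significant suicide risk and MADRS above 30 are exclusions, although the phone screen comes before these are applied.

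Ideation raised in therapy sessions is outside this point; the visible text for therapists sets no in-person rule. The conclusion assumes that no unseen figure supplies an off-site route.

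**What to change.** 1. Reword the active branch's Step 2, for example: *The clinician sees the patient face to face when on site; when the patient is elsewhere, the clinician evaluates by phone or video, preferably within the same contact.* Leave Step 4's order as it is (supervising clinician, attending, then 911). Step 2 should not carry its own 911 clause, which would come ahead of those fallbacks.
2. Under the hospitalisation instructions in both branches, add for both sites: *For an off-site patient, confirm where the patient is now, stay on the line, call 911 to that location and pass the clinical information to EMS.*

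The cost is amendment wording and brief retraining of RAs and clinicians, with no new visits, staff or instruments. The drawback is that a remote evaluation shows the clinician less than a face-to-face one, which is why in person stays the rule on site.
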